#### **Background, Significance and Rationale**

#### Background, Significance and Rationale

Cannabis use is increasing and numbers are likely to rise further with legalization (Hasin et al., 2015). Currently, approximately 24% of patients entering treatment for a substance use disorder have cannabis use disorder (CUD; SAMHSA, 2013), yet their outcome is poor (MTPRG, 2004; Budney et al., 2006; Kadden et al., 2007; Levin et al., 2011, 2015). There is a clear need for FDA-approved pharmacological options to improve cannabis treatment outcome.

The purpose of this study is to test the effects of the benzodiazepine, clonazepam, as a potential treatment for CUD. The rationale for testing a benzodiazepine is the following: Cannabis withdrawal is, in part, characterized by symptoms such as anxiety and disordered sleeping (Haney et al., 1999, 2005; Budney et al., 2004), and clonazepam is efficacious and used therapeutically to treat both of these symptoms. Although benzodiazepines have the potential for abuse, clonazepam has a long half-life and is less reinforcing that fast-onset benzodiazepines (alprazolam, lorazepam) so was selected to be a time-limited treatment to facilitate the transition from regular cannabis use to abstinence.

Nonetheless, clonazepam is a controlled substance, and its administration to patients with a substance use disorder requires careful monitoring and minimization of the potential risks for misuse and physiological dependence. During the inpatient study period, study medication will be distributed on a single dose basis. During the outpatient period, study medication (clonazepam vs. placebo), will be distributed at weekly intervals and pill counts and biological measures of medication compliance (e.g., quantitative riboflavin) will be performed. The overall time period of potential exposure to clonazepam will be 8 weeks, with a 4 week time medication-free observation period following taper and discontinuation of study medication. These study features should minimize the risk of exposing individuals with CUD to clonazepam.

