We will emphasize at each visit the importance of not stopping medication use abruptly. If participants wish to stop or use less medication at any point, we will initiate a taper with them. This outcome will be part of our secondary endpoint (medication adherence and tolerability).

*Medication:* Clonazepam and matching placebo will be prepared by our pharmacy at the NYSPI, packaged in matching gelatin capsules with lactose filler in each capsule. The research pharmacist, who has no contact with patients, is the only non-blind member of the research team. At each weekly visit the psychiatrist orders the dose of double-blind medication for the coming week according to the schedule (Table 2). The psychiatrist will adjust the dose according to tolerability. Clonazepam or matching placebo will be given in a fixed-flexible dose schedule with clonazepam dose titrated to 2mg per day or the maximum tolerated dose.

Clonazepam or matching placebo will be taken twice per day in the morning and in the evening. The medication will be packaged in gelatin capsules with lactose filler plus 12.5mg of riboflavin. Clonazepam or matching placebo are given in a "fixed flexible" dose schedule with the dose titrated to 2mg per day or the maximum tolerated dose.

If a patient does experience any uncomfortable side effects, the dose will not be raised, and if necessary, the dose will be lowered. If the patient cannot tolerate at least 0.5mg/day of clonazepam, the medication will be discontinued.

Planned/unplanned absences that would require the patient to be given more than one week worth of medications will be considered on a case-by-case basis. In the case of unplanned absences, up to one week of medication can be shipped via Fedex with signature upon receipt. This will allow patient who miss their scheduled appointments to remain on stable medication.

*Medication Taper*: During week 8, study medication will be tapered gradually to off (see table 2). This gradual discontinuation of study medication will minimize the discontinuation effects for participants exposed to clonazepam over the prior 7-week study period. For individuals exposed to clonazepam (a BZD with a long half-life) for a seven week period, a one week taper of study medication will be adequate to avoid the risk of physiological withdrawal. Participants will be monitored for the development of BZD withdrawal during and after the taper period, and will be managed clinically if significant withdrawal

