symptoms emerge. It is unlikely that the length of time participants are exposed to clonazepam during the protocol will result in the development of physiological dependence that makes discontinuation difficult. However, there may be cases where participants due experience difficulty with the length of the taper schedule. If clinically significant withdrawal symptoms emerge during the taper, the taper may be extended for a second week based on clinical judgment by the study psychiatrist.

We will evaluate the adequacy of the double-blind by asking patients which treatment drug they think they are receiving. The blinded nurse will also be asked to report which drug s/he thinks each patient is taking. The research staff that administers medication and/or conducts interviews and assessments will be blind to medication condition, urine toxicology results, and medication blood levels during the course of the 12-week trial. The non-blinded pharmacist will be the only ones who have access to this information during the trial. However, a sealed envelope will be kept in the locked office if the Principal Investigator needs to break the blind in an emergency situation. At the completion of the 12 week trial, or at the conclusion of the patient's involvement in the trial (if they do not complete all 12 weeks), patient will learn their treatment assignment.

The medication capsules will contain riboflavin. This non-harmful substance will allow the clinic to verify that the study medication is being taken correctly and absorbed by the body. The urine samples obtained twice per week will be examined for riboflavin. In addition, folic acid in the form of a 1mg "pill" will be added to all placebo capsules in an attempt to improve the blind. The patient will receive up to 2mg of folic acid daily. Patients will receive medication in non-childproof packaging.

*Medication Adherence Enhancement*: We will use a combination of the quantitative fluorometric riboflavin determination method developed by our research group (Herron et al. 2013), timeline followback interview, and pill count with a weekly financial incentive (\$10) for medication bottle return to both enhance and measure medication adherence. Note, participants will be instructed to take their morning capsules and come to the clinic within 6-8 hours to ensure that riboflavin levels will be detectable.

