## **Risks/Discomforts/Inconveniences**

Risks that could be encountered during the study period **Potential Risks** 

There are risks associated with benzodiazepine misuse, withdrawal and overdose. The more severe withdrawal symptoms have usually been limited to those patients who received excessive doses over an extended period of time. Generally milder withdrawal symptoms (e.g., dysphoria and insomnia) have been reported following abrupt discontinuance of benzodiazepines taken continuously at therapeutic levels for several months. Misuse or taking benzodiazepines for long periods of time may lead to a drug habit, where a patient could become dependent on a benzodiazepine, such as clonazepam, to function. Benzodiazepines are commonly misused and have a potential for abuse. They can have harmful effects and are easily available. Death and serious illness rarely result from benzodiazepines, such as clonazepam; however this medication can be dangerous when taken with either alcohol or other medications. The combination of substances can even cause death. The most common adverse reactions noted with clonazepam are: drowsiness, confusion, dizziness, difficulty concentrating and loss of memory. Participants will be cautioned against driving a car or operating machinery, and will be warned against stopping the medication abruptly or drinking alcohol while participating in the study. We will also closely monitor for abuse-related behavior, both in our rating scales and in our weekly clinical visits.

An additional of risk of research participation is cannabis withdrawal, e.g., irritability, anxiety, disruptions in sleep and/or food intake. All participants are fully informed of the side effects that they might experience, and because all currently smoke cannabis, these effects should be familiar to them. Finally, the combination of clonazepam and cannabis may have additive intoxicating effects. The research psychiatrist will discuss misuse, withdrawal, and risks of overdose with each participant.

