## Table 3: Outpatient Study Assessments

	X once weekly; XX twice weekly	Screening	Baseline	Week 1	Week 2	Week 3	Week 4	Week 5	Week 6	Week 7	Week 8	Week 9	Week 10	Week 11	Week 12
	Medical History and Physical Examination	x													
	Pregnancy, serum	x													
	Pregnancy, urine		x				х				х				х
	Psychiatric Evaluation	x													
5	Serum Laboratory Examination	x					х				х				х
latic	Urinalysis	x					х				х				х
Medical Evaluation	Urine Toxicology	x	x	х	X X	x x	x x								
dical	Urine Fluorometry (quantitative riboflavin)			x	X X	X X	x x								
Med	Vital signs (weight, pulse, blood pressure, and temperature)		x	x	X X	x x	x x								
	CIWA-BZD									Х	Х	Х	Х		
	Clinical Global Improvement Scale (CGI)- Observer		x	х	x	x	х	х	x	x	х	x	х	x	x
	C-SSRS	x	x		x		х		х		х		х		х
	Hamilton Anxiety Scale (HAM-A)		x		x		х		х		х		х		х
Interview	MINI International Neuropsychiatric Interview	x													
ter	Structure Pill Count Interview			х	x	x	х	х	х	x	х	х	х	х	х
_	Systematic Assessment for Treatment and Emergent Events (SAFTEE)		x	x	x	x	x	x	x	x	x	x	х	x	x
	Timeline Follow-Back (TLFB)	x	x	х	x	x	х	х	х	x	х	х	х	х	х
	Treatment Services Review (TSR)		х	х	x	x	х	х	х	x	х	х	х	х	х
	Clinical Global Impression (CGI)-Self		x	х	x	x	х	х	x	х	х	х	х	х	х
Self- Report	Marijuana Craving Questionnaire (MCQ)		х	х	x	x	х	х	х	x	х	х	х	х	х
Se Rep	Marijuana Withdrawal Checklist (MWC)		x	х	x	x	х	х	x	x	х	х	х	х	х
	Pittsburgh Sleep Quality Index (PSQI)		х	х	х	х	х	х	х	х	х	х	х	х	х

Tabl	e 1: Inpatient F					
Day	1	2	3	4	5	6
Study Groups	Move-in	Witha	Irawal, cognition	, abuse liability		Move-out
Clonazepam (mg/day)	1.0	2.0	2.0	2.0	2.0	2.0
Placebo (mg/day)	0.0	0.0	0.0	0.0	0.0	0.0

Study Groups	Week 1 Days 6-7 (outpatient)	Weeks 2-7 Days 8-49 (outpatient)	Week 8 Days 50-51 (outpatient taper)	Week 8 Days 52-54 (outpatient taper)	Week 8 Days 55-56 (outpatient taper)	Week 9-12 Days 57-84 (outpatient obervations)
Experimental Group	clonazepam capsules 1 mg twice daily	Clonazeapam capsules 1 mg twice daily	Clonazepam capsules 0.5 mg QAM and 1 mg QHS	Clonazepam capsules 0.5 mg QAM and 0.5 mg QHS	Clonazepam capsules 0.5 mg QHS	No study medication
Placebo Group	Placebo capsules Twice daily	Placebo capsules twice daily	Placebo capsules twice daily	Placebo capsules twice daily	Placebo capsule QHS	No study medication

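### The protocol sends clonazepam home each week in non-childproof packaging for every patient, without giving a reason; a child-resistant bottle would be a cheap safety improvement.

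*Protocol*

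**What the plan says.** The packaging rule is one sentence in the protocol's Study Procedures, at the end of the paragraph on riboflavin and the placebo capsules: "Patients will receive medication in non-childproof packaging". It carries no condition, such as a patient's request or difficulty with closures, and no explanation.

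The other relevant statements in the protocol are these.

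- **Take-home supply.** Background, Significance and Rationale says that in the outpatient period "study medication (clonazepam vs. placebo), will be distributed at weekly intervals".
- **Larger supplies.** Study Procedures adds: "Planned/unplanned absences that would require the patient to be given more than one week worth of medications will be considered on a case-by-case basis".
- **Shipping.** The same paragraph says that for unplanned absences "up to one week of medication can be shipped via Fedex with signature upon receipt".
- **Scheduled dose.** The outpatient dosing table (Table 2, printed after Table 3) gives, for weeks 2 to 7, "Clonazeapam capsules 1 mg twice daily".
- **Risk statement.** Risks/Discomforts/Inconveniences opens with "There are risks associated with benzodiazepine misuse, withdrawal and overdose".
- **Container.** Study Procedures and Compensation and/or Reimbursement describe a medication bottle that patients are paid $10 a week to return, up to $80 in total.

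**The concern.** The rule removes an ordinary barrier between a sedative and anyone else in the home, and it does so for all patients by default. Eligibility is open to adults aged 18 to 65 and does not consider who lives with them, so some homes may include children.

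The controls described in the protocol are aimed elsewhere. Weekly dispensing, pill counts and riboflavin testing address misuse, dependence and adherence in the patient. A pill count can show that capsules are missing only after the event.

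What is at stake is an accidental ingestion by a child or other household member. Because the capsules are blinded, the household would not know whether they contained clonazepam or placebo. No result of the trial depends on this.

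**Working it through.** The plan states no figure on this point, so there is none to reproduce. The check has two parts: how much drug is in the home, and whether anything in the described procedures needs this packaging.

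**Inputs**
- Scheduled dose in weeks 2 to 7: 1 mg twice daily (protocol, Table 2).
- Dispensing interval: 7 days (protocol, Background).
- Lowest dose at which medication continues under the flexible schedule: 0.5 mg/day (protocol, Study Procedures).
- Taper in week 8: 1.5 mg/day for 2 days, 1.0 mg/day for 3 days, 0.5 mg/day for 2 days (protocol, Table 2).
- Active-arm size: 40 (SAP, A4).

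**Amount in the home at the start of a week**
1. Full scheduled dose: 7 days × 2 doses × 1 mg = 14 mg. This is 14 capsules if each dose is one capsule.
2. Lowest continuing dose: 7 × 0.5 mg = 3.5 mg.
3. Taper week, if supplied at once: 2 × 1.5 + 3 × 1.0 + 2 × 0.5 = 3 + 3 + 1 = 7 mg.
4. More than one week's supply: above 14 mg at the full dose. The protocol sets no upper limit. If two weeks were given (an assumption for illustration), it would be 2 × 14 = 28 mg.

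The amount falls each day as capsules are taken, so 14 mg is the usual peak rather than an average.

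**Number of homes**

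Up to 40 homes hold clonazepam. The other 40 of the 80 hold placebo. The share with children is not given, so no event probability can be calculated.

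**Does any described procedure need the packaging?**
- *Blind.* It rests on matching gelatin capsules, lactose filler, riboflavin in the capsules and folic acid in the placebo. The closure plays no part, provided both arms have the same one.
- *Adherence.* Pill count, bottle return and urinary riboflavin work with any closure.
- *Container.* The weekly payment of $10 and the maximum of $80 imply 80 / 10 = 8 bottle returns, which matches the 8 medication weeks. A returnable bottle is already in use, so only its closure would change.

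No described procedure depends on easy-open packaging.

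**The case against.** The best case on the other side is that this is a disclosed packaging choice which contradicts nothing in the protocol, and that an unstated reason is not the same as no reason. Ease of opening is a plausible one. Shipment is limited to one week and needs a signature, and weekly dispensing with paid bottle return limits what builds up at home. All of this stands, and it keeps the point modest. It does not supply a reason for applying the rule to every patient.

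A reader might infer several stronger things that the documents do not support.

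- **That the protocol calls the household risk potentially lethal.** The Risks section does say "this medication can be dangerous when taken with either alcohol or other medications. The combination of substances can even cause death". That concerns a user who combines substances, and the same sentence begins "Death and serious illness rarely result from benzodiazepines, such as clonazepam". Nothing there describes or measures accidental ingestion by a child.
- **That the packaging breaks the protocol's own commitment to minimise risk.** The Background commitment concerns misuse and dependence in enrolled patients. The statement under Protection Against Risk is general. Neither addresses other people in the home.
- **That 95 mg is at hand.** The schedule for days 6 to 56 does total 44 × 2 + 7 = 95 mg, but that is cumulative over 51 days, and some of the day 6 dose may be given on the unit.
- **That 80 homes are exposed.** Placebo homes hold no clonazepam.
- **That patients receive no storage advice.** The available risk and patient-education sections give none. The consent pages were not available, so advice there cannot be ruled out. The point rests on the packaging sentence alone.
- **That the packaging has no benefit.** All that can be said is that no benefit is stated.

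**Conclusion.** The point holds as a cheap safety improvement. The protocol specifies non-childproof packaging for all patients without a reason, for a take-home sedative with a stated overdose risk. At the scheduled dose the exposure is about 14 mg of clonazepam at the start of a week, in up to 40 homes. It is less for patients on a reduced dose and more where a larger supply is allowed.

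This assumes weekly dispensing at the full scheduled dose and 40 patients on active drug. The likelihood of an accidental ingestion is unknown, because nothing is said about household composition. The point has no bearing on the endpoints, power, analysis or interpretation of the trial.

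**What to change.** Amend the packaging sentence in Study Procedures so that the same blinded capsules are dispensed and shipped in child-resistant bottles in both arms, with a documented exception for a patient who cannot open them. If the sponsor has a reason for the present packaging, the protocol should state it and limit the packaging to the patients to whom the reason applies.

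Using one closure for both arms protects the blind. Bottle return, pill count, riboflavin testing, dose and schedule are unchanged.

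The cost is one amended sentence, a minor change in what the pharmacy stocks and slightly less convenient opening. The documents do not describe the pharmacy's supplies, so that it can make the change easily is an assumption to confirm.

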## **Criteria for Early Discontinuation**

Criteria for Early Discontinuation

## Patient Monitoring and Removal from the Study during Outpatient Phase

The psychiatrist and/or therapist will assess appropriateness for continuation in the research study on a

continuous basis, and will remove from the trial patients with significant clinical deterioration or noncompliance of a type that could be dangerous. Criteria for removal from the study will include:

1. Development of serious psychiatric symptoms as indicated by a Clinical Global Impression (CGI) improvement score of 6 (much worse than baseline) or greater for 2 consecutive weeks.

2. If the participant's continued cannabis use places him or her at risk for self-destructive behavior or other harm as indicated by a CGI improvement score of 6 (much worse than baseline) or greater for 2 consecutive weeks.

3. Development of serious medical conditions that may or may not be related to study participation (e.g., vital sign measurements, and monthly serum and urine laboratory studies.)

4. If the participant becomes pregnant as assessed by monthly urine pregnancy testing.

In case that the patient is removed from the research trial for medical reasons, or is requesting withdrawal from the study, he/she will be retained in open treatment for the remaining of the study period. Upon removal of a patient from the trial due to clinical deterioration, the patient will be referred for appropriate follow-up treatment, in most instances either intensive outpatient or residential treatment. The PI or a study psychiatrist is available 24 hours/day by phone and/or beeper in case of emergency.

## Blood and other Biological Samples

Please create or insert a table describing the proposed collection of blood or other biological specimens Approximately 20 ml of blood (4 teaspoons) will be drawn at the time of baseline assessment, weeks 4, 8, and study completion for routine analyses (hematology, blood chemistry (including liver function tests), and blood pregnancy test for women). They may be repeated during the study if clinically indicated. Approximately, 80 ml of blood will be drawn overall (i.e., baseline, weeks 4, 8, and study completion = 4 x 20 ml = 80 ml).

Quantitative urine toxicology screens for THC with Creatinine will be conducted at each visit (2 per week) and serve as an objective marker of current cannabis use.

HIV testing will be offered in order to determine the HIV status of all possible participants; participants may refuse if they do not want to be tested. Nursing staff will provide Pre and Post-test counselling to assist participants with any HIV+ results. Pre-HIV test counselling discusses the possibilities of a HIV+ test and the procedures after a positive HIV test is found. Post-HIV counselling assesses for suicidal and/or homicidal ideation, along with domestic violence issues. If a person tests positive for HIV, the research psychiatrist on staff with be notified and will do a secondary evaluation for necessity of immediate psychiatric care. Additionally the nursing staff will notify the department of health and provide a list of referrals for follow-up care.

A confirmatory HIV test will not routinely be done due to the accuracy of the saliva quick test, however if a participant tests positive using the saliva quick test a confirmatory blood test will immediately be done.

#### **Assessment Instruments**

Create a table or give a brief description of the instruments that will be used for assessment Ongoing Psychiatric and Medical Assessments: The research psychiatrist will conduct weekly assessments of the psychiatric and medical status of the study participants. Participants taking psychotropic medications will be excluded. Participants who meet criteria for clinical worsening (e.g., CGI improvement >5 two weeks in a row) or the development of unacceptable medical or psychiatric risks will be removed from the trial and referred for appropriate treatment.

#### **Outpatient Study Assessments**

Adverse Effects measures: The Systematic Assessment for Treatment and Emergent Events (SAFTEE; Johnson et al. 2005) adapted for clonazepam will be performed weekly to identify adverse symptoms. Benzodiazepine withdrawal measure: The Clinical Institute Withdrawal Assessment-Benzodiazepines (CIWA-B)(Busto, 1989) is a 22-item scale to assess the degree of benzodiazepine withdrawal. Cannabis Craving measure: The Marijuana Craving Questionnaire (MCQ) is a 47-item instrument (Heishman et al. 2001).

Columbia Suicide Severity Rating Scale: Will be used to monitor suicidality at baseline and twice a month during the study period.

Medical Evaluation and Monitoring: A medical history and physical exam will be performed during screening. Serum pregnancy testing will be performed during screening and urine pregnancy testing will be performed monthly during the study. Complete blood count, electrolyte, urinalysis and liver function tests will be performed during screening and monthly during the study. Height and weight will be measured and baseline body mass index (BMI) calculated during screening. Temperature, pulse, blood pressure, and weight will be measured at every study visit.

Cannabis Use Outcome measures: Cannabis use will be recorded by the timeline followback (TLFB) method (Litten and Allen 1992) modified for cannabis and confirmed by creatinine-normalized quantitative urine THC levels. Other substance (including nicotine and alcohol) use self-report data will also be gathered during the TLFB interview. Urine samples for quantitative urine THC levels and creatinine will be collected under directly-observed conditions during screening and at each study visit (twice weekly). Creatinine levels can be used to control for urine concentration variability and screen for adulterated samples. Creatinine-corrected quantitative urine THC levels will then be used to confirm self-reported cannabis use, using a method similar to that described by Preston et al. (Preston et al. 1997) for cocaine dependence, where an obvious pattern of new use (i.e., level more than doubles in the past two days) overrides a self-report of no use.

Cannabis Withdrawal measure: We will use the 22-item version of the Marijuana Withdrawal Checklist (MWC; Budney et al. 1999) that measures subject-rated severity as the primary outcome measure of withdrawal.

*Clinical Status*: The Clinical Global Impression Scale-Observer (CGI; Guy 1976) will be used to measure the overall clinical status of the participant as well change from baseline in symptom severity. The Clinical Global Impression-Self (CGI-S) is a two-item scale that asks the subject to rate his or her current level of symptoms and estimate changes from baseline (Guy 1976).

Cognitive, Behavioral and Impulsivity Measures: A series of cognitive and behavioral measures will be performed at baseline, end of active medication treatment (week 8), and end of the observation period (week 12), to explore potential therapeutic mechanisms of action of the medication treatment.

Concurrent Treatment measure: The Modified Treatment Services Review assesses the past-week exposure to health care, psychiatric, or substance use disorder treatment (McLellan et al. 1992).

Medication Adherence measures: The Structured Pill Count Interview is a timeline followback assessment of study medication compliance accounting for each dose of prescribed study medication. Fluorometric detection of a urinary riboflavin concentration (Herron et al. 2013) will be used as a biological method to determine compliance with study medication.

Anxiety measure: A structured-interview version of the Hamilton Anxiety Scale (HAM-A; Hamilton 1959) will be used to assess mood and anxiety symptoms at baseline and changes associated with treatment.

Psychiatric Evaluation and Diagnosis: The MINI International Neuropsychiatric Interview will be performed during screening as part of a complete psychiatric diagnostic assessment.

Sleep measure: The Pittsburgh Sleep Quality Index Scale (PSQI; Buysse 1989) will be the primary outcome of sleep quality and length.

Please attach copies, unless standard instruments are used outpatient study assessments 5-24-16.pdf

